### 11.2. Prior and Concomitant Medication Review

See [Section 10.3](#) for a complete description of medications permitted during the study. Site study staff will record all medications used to treat schizophrenia taken within 6 months prior to screening visit in the eCRF. Also, the following parameters will be recorded for all concomitant medications: drug name, route of administration, total daily dose, unit, frequency, start/stop dates, indication, and whether the medication was started after last dose of study medication. The prior and concomitant medications will subsequently be coded using the World Health Organization Drug Dictionary (WHO-DD).

### 11.3. Structured Clinical Interview for DSM-5 Axis I Disorders-Clinical Trials version (SCID-CT)

The SCID-5-CT is a modified version of the SCID developed for use in clinical trials. It is a semi-structured interview for the purpose of making a DSM-5 diagnosis ([First-2015](#)). Clinicians administering the SCID should be familiar with the DSM-5 classification and diagnostic criteria. The SCID-5-CT will be administered by a qualified rater at the research site listed on Form FDA 1572 with at least 2 years of experience with the population under study. The administration time is approximately 30 - 40 minutes.

### 11.4. PET/fMRI Assessments

It is important that the participant is examined under the same conditions at baseline and subsequent scan, including scanning at the same time of day where possible (scanning time of day should be  $\pm$  3h from the time of day of the baseline scan where possible), and head motion monitored and minimised. The post-dose scan should be timed to occur so that the start is approximately at the time in which maximum observed plasma concentration ( $C_{max}$ ) occurs. Post dose fMRI scanning will start approximately 2 to 4 hours after dosing.

Prior to entry into the scanner, subjects will complete the site's standard radiography screening questionnaire to ensure they are safe to enter the scanner environment (eg, no history of surgery involving metal implants). Females will undergo urine pregnancy test to exclude pregnancy. Scan date as well as start and stop time will be collected.

Approximately 1 hour before the scan participants will receive 150 mg of carbidopa and 400 mg of entacapone orally. This inhibits the formation of radiolabeled metabolites of F-DOPA that may cross the blood-brain barrier, and boosts the signal to noise ratio. Subjects will have an IV canula placed in the ante-cubital fossa for administration of F-DOPA. Prior to scanning they will be asked to go to the toilet.

Striatal dopamine synthesis capacity (DSC) assessment ( $K_i$ ) using  $^{18}\text{F}$ -DOPA kinetic analysis will be performed.

In addition to fMRI scan sequences, exploratory MRI sequences may be performed during each of the MRI and PET/MR acquisition times and may include (but not limited to) a neuromelanin-sensitive MRI (NM-MRI) sequence and an iron-sensitive MRI sequence (effective transverse relaxation rate [ $R_2^*$ ] or Quantitative Susceptibility Mapping [QSM]). Repeat MRI including exploratory MRI sequences may be performed where it is not possible to obtain complete measures during the PET-MRI scan.

The majority of participants will receive up to 2 PET scans. Participants will only receive 3 PET scans in the event that a scan is not able to be completed or is not suitable for analysis.

## **11.5. Efficacy Assessments**

### **11.5.1. Positive and Negative Syndrome Scale (PANSS)**

The PANSS is an interview-based measure of the severity of psychopathology in adults with psychotic disorders. The measure is comprised of 30 items and 3 scales: the Positive scale assesses hallucinations, delusions, and related symptoms; the Negative scale assesses emotional withdrawal, lack of motivation, and similar symptoms; and the General Psychopathology scale addresses other symptoms such as anxiety, somatic concern, and disorientation. An anchored Likert scale from 1 - 7, where values of 2 and above indicate the presence of progressively more severe symptoms, is used to score each item. Individual items are then summed to determine scores for the 3 scales, as well as a total score. A Composite scale score (Positive scale score minus Negative scale score) can also be calculated to show the relative valence of positive and negative symptoms. Total time required for the PANSS interview and scoring is approximately 30 - 40 minutes ([Kay-1994](#), [Opler-1992](#); [Perkins-2000](#)). PANSS raters will be required to meet specific training and education criteria before they are certified to rate for this study. In addition, raters will receive specific training and education regarding all of the assessments prior to study initiation.

### **11.5.2. Brief Negative Symptom Scale (BNSS)**

The BNSS is a rating scale to measure the current level of severity of negative symptoms in schizophrenia and schizoaffective disorder. The measure is comprised of 13 individual items and 5 domain scores (blunted affect, alogia, avolition, anhedonia, and asociality). The 5 domain scores provide a summary score and the 13 individual items provide a composite total score (ranging from 0 to 78). Each of the items are scored on a Likert-type 7-point scale from 0 - 6,

where values of 0 indicates symptom is absent and a value of 6 means the symptom is a severe form. The number of items varies per domain. BNSS raters will be required to meet specific training and education criteria before they are certified to rate for this study. In addition, raters will receive specific training and education regarding all of the assessments prior to study initiation.

#### **11.5.3. Montgomery-Asberg Depression Rating Scale (MADRS)**

The MADRS is a clinician-rated assessment of the subject's level of depression. The measure contains 10 items that measure apparent and reported sadness, inner tension, reduced sleep and appetite, difficulty concentrating, lassitude, inability to feel, and pessimistic and suicidal thoughts. Each item is scored in a range of 0 to 6 points, with higher scores indicating increased depressive symptoms. The Structured Interview Guide for the MADRS (SIGMA) ([Williams-2008](#)) will be used for the administration of the MADRS assessment. The MADRS will be administered by a qualified rater at the site.

#### **11.5.4. Clinical Global Impressions – Severity Scale (CGI-S)**

The CGI-S is a clinician-rated assessment of the subject's current illness state on a 7-point scale, where a higher score is associated with greater illness severity. Following a clinical interview, the CGI-S can be completed in 1 to 2 minutes. The CGI-S will be administered by a qualified rater at the site.

### **11.6. Safety Assessments**

The Investigator or appropriate designee will review results of safety assessments on a regular basis and the Sponsor must be kept fully informed of any clinically significant findings either at Screening or subsequently during study conduct.

#### **11.6.1. Adverse Events**

Adverse events will be collected for each subject. Subjects should be queried in a non-leading manner, without specific prompting (eg, "Has there been any change in your health status since your last visit?"). See Section 12, Safety Reporting.

AEs and SAEs will be monitored throughout the study at all visits.

#### **11.6.2. Clinical Laboratory Assessments**

The clinical laboratory tests required by protocol are listed in [Section 21](#), Appendix II.

Blood and urine samples will be collected for clinical laboratory tests. All clinical laboratory tests will be performed locally. For detailed instructions regarding clinical laboratory procedures, sampling, and shipping guidelines refer to the study center and local clinical laboratory guidelines. Samples will be processed at a local laboratory. Out of range laboratory results assessed as clinically significant by the investigator will be reported as adverse events.

### **11.6.3. Vital Signs**

Vital sign measurements consist of systolic and diastolic blood pressures, respiratory rate, pulse rate, and oral temperature.

Blood pressure and pulse rate should first be taken with the subject in the supine position after resting for  $\geq 5$  minutes. Blood pressure and pulse rate will be taken again after standing for 2 to 4 minutes. The same arm should be used during each assessment of blood pressure and pulse rate throughout the study. If a subject develops symptoms consistent with orthostatic hypotension (light-headedness, dizziness, or changes in sensorium upon standing) at any point, his or her supine and standing blood pressure and pulse rate should be collected at that time in the manner described above. Vital signs results assessed as clinically significant by the investigator will be reported as adverse events. Vital signs will be obtained prior to clinical laboratory collection and performance of an ECG.

### **11.6.4. Electrocardiograms (ECGs)**

Subjects will be supine for at least 10 minutes prior to and 5 minutes after the ECG is obtained. ECGs will be 12-lead with a 10-second rhythm strip. ECGs should be obtained prior to drawing blood samples. All attempts should be made to use the same ECG recorder for all visits within individual subjects. Refer to [Section 20](#), Appendix I for additional information. ECG parameters to be collected include ventricular heart rate (beats/min), QT interval (msec), PR interval (msec), QRS interval (msec), RR interval (msec), and overall ECG interpretation (Normal, Abnormal NCS, Abnormal CS).

It is the responsibility of the Investigator to perform a safety review of the ECG data for changes from previous assessments and/or emergent cardiac dysfunction, and to determine subjects' eligibility for or continuance in the study. Abnormalities require comment as not clinically significant (NCS) or clinically significant (CS). Typically, CS designated events will be reported as adverse events.

ECGs will be reviewed, signed and dated by the Investigator after each ECG collection. The same physician should review all ECG reports for a given subject whenever possible.

The original ECG tracing will be kept with subject's source documentation. A copy may be collected by the Sponsor.

### **11.6.5. Physical and Neurological Examination**

A full PE as well as a neurological will be performed. The PE includes an assessment of general appearance and a review of systems (dermatologic, head, eyes, ears, nose, mouth/throat/neck, thyroid, lymph nodes, respiratory, cardiovascular, gastrointestinal, extremities, musculoskeletal, neurologic, and psychiatric systems).

All PE and neurological exam findings at screening will be captured in the medical history in the CRF. Any clinically significant changes from screening, as determined by the Investigator, will be noted as AEs in the CRF.

### **11.6.6. Height, Weight, and BMI**

Weight will be measured in kilograms as specified in the schedule of assessments ([Table 2](#)). Height in meters will be recorded only at Screening.

Height will be measured without shoes.

Weight will be measured in street clothes, without shoes and coat/jacket.

BMI will be calculated by site staff using the equation  $BMI = \text{weight [kg]}/\text{height [m]}^2$  at Screening only. BMI for all other visits will be derived within the Electronic Data Capture (EDC) system.

### **11.6.7. Safety Scales**

#### **11.6.7.1. Abnormal Involuntary Movement Scale (AIMS)**

The AIMS is a clinician-rated assessment of abnormal movements consisting of unobtrusive observation of the subject at rest (with shoes removed) and several questions or instructions directed toward the subject. Using a severity scale ranging from 0 (none) to 4 (severe), clinicians rate dyskinesia in several body regions, including the facial area, extremities, and trunk. There are two items related to dental status, as well as three global impression items assessing overall severity, incapacitation, and the subject's awareness of abnormal movements ([Guy-1976](#); [Munetz-1988](#)). The AIMS raters will be required to meet specific credential and educational criteria before they are certified to rate for this study. The AIMS will be administered by a qualified rater at the site.

#### **11.6.7.2. Barnes Akathisia Rating Scale (BARS)**

The BARS is a rating scale geared toward assessment of neuroleptic-induced akathisia, though it can be used to measure akathisia associated with other drugs as well. The BARS consists of four items, including one item assessing objective restlessness, two items targeting subjective restlessness (awareness and related distress), and one global clinical assessment item. All items are anchored and utilize a 4-point scale, except for the global rating which has a 6-point scale (from absence of akathisia through severe akathisia). The subjective and objective items are summed to yield a total score. The BARS can be administered in about 10 minutes ([Barnes-1989](#); [Barnes-2003](#)). The BARS will be administered by a qualified rater at the site.

#### **11.6.7.3. Simpson-Angus Scale (SAS)**

The SAS is a clinician-rated assessment of neuroleptic-induced Parkinsonism consisting of 10 items. Items are anchor-based, rated on a 5-point scale of severity, and address rigidity, gait (bradykinesia), tremor, akathisia, shoulder shaking, glabellar tap, and salivation ([Siddiqui-2009](#); [Simpson-1970](#)). The SAS will be administered by a qualified rater at the site.

#### **11.6.7.4. Columbia Suicide Severity Rating Scale (C-SSRS)**

The C-SSRS is a tool designed to systematically assess and track suicidal adverse events (suicidal behavior and suicidal ideation) throughout the trial. The strength of this suicide classification system is in its ability to comprehensively identify suicidal events while limiting the over-identification of suicidal behavior. The scale takes approximately 5 minutes to

administer. The C-SSRS will be administered by a trained rater at the site. Subjects with Type 4 or Type 5 suicidal ideation during the study will be discontinued from the study and referred to a mental health professional ([Posner-2007](#)). At screening visit, “Baseline/Screening” version of C-SSRS will be used including assessment for lifetime and previous 1 month. For all visits from Visit 2 onward, the “Since Last Visit” version of the C-SSRS will be used.

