j Blood samples for antipsychotic plasma concentrations will be collected at Screening, Day -2, Day 1 (approximately 10 minutes prior to dosing), Day 2 (2 - 4 hours postdose), Day 7 (2 – 4 hours postdose), Day 14 (prior to PET scan), and at Follow-up.

k Additional urine drug screen may be ordered as deemed clinically appropriate. These results should be discussed with the Medical Monitor.

l Each PET scan will be accompanied by intravenous administration of radiotracer  $^{18}\text{F}$ -DOPA and oral pre-treatment (1 hour prior to tracer) with 150 mg carbidopa and 400 mg entacapone. If PET/MR scanner is unavailable for technical reasons separate PET and MR scans (on an alternate PET scanner without MR and alternate MR scanner) will be permitted. Prior to each PET scan, there is a period of resting state fMRI collection. In addition to fMRI scan sequences, exploratory MRI sequences may be performed during each of the MRI and PET/MR acquisition times and may include (but not limited to) a neuromelanin-sensitive MRI (NM-MRI) sequence and an iron-sensitive MRI sequence (effective transverse relaxation rate [R2\*] or Quantitative Susceptibility Mapping [QSM]). Repeat MRI including exploratory MRI sequences may be performed where it is not possible to obtain complete measures during the PET-MRI scan.

m In the event of unsuccessful PET scan on Day 14, additional days of dosing may be necessary up to, but not exceeding, Day 19. If any such additional days are necessary, subjects will continue their usual daily dosing. PANSS, BNSS, MADRS, and CGI-S may be assessed  $\pm 1$  day of PET scan; other assessments are to be completed the same day as the PET scan. Participants will only receive 3 PET scans in the event that a scan is not able to be completed or is not suitable for analysis. It is expected that the majority of participants will receive up to 2 PET scans which would result in an effective dose of 7.4 mSv.

n PET scan to be performed at early termination (ET) visit only if the subject terminates the study prior to Day 14 PET scan.

o Only perform PANSS, BNSS, CGI-S, and MADRS if subject discontinues prior to Day 14 scan day.

p At the screening visit, the “Baseline/Screening” version will be completed; the “Since Last Visit” version of the C-SSRS will be administered for all other visits. C-SSRS should be performed prior to PET scan on Day 14.

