q Unscheduled BARS, AIMS, and SAS scales should be administered if a subject develops extrapyramidal symptoms (EPS) requiring treatment.

r All adverse events occurring after signing informed consent through the end of study will be collected.

s PANSS, BNSS, MADRS, CGI-S, and C-SSRS to be completed on Day -2 or Day -1.

t BARS, AMES, SAS to be collected on Day -1 or Day 1 (predose).

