**Figure 1: Study Schematic**

a Dose reduction to 50 mg/day allowed for reasons of tolerability.

b Subject must remain in-clinic and on treatment until completion of the Visit 2 assessments, including scans. In the event of an unsuccessful PET scan on Day 14, additional days of dosing may be necessary up to, but not exceeding, Day 19.

Prior to each PET scan, there is a period of resting state fMRI collection. Two PET scans will be conducted during the study: 1 PET scan prior to dosing (between Day -44 to Day -2) and 1 PET scan following approximately 14 days of treatment (Day 14).

Safety and tolerability will be monitored throughout the study by physical examination, ECGs, vital signs, body weight, BMI, collection of AEs, clinical laboratory parameters, and the Columbia-Suicide Severity Rating Scale (C-SSRS). Subjects who have significant findings for suicidal ideation assessed by the C-SSRS at any time during the study must be referred to the Investigator for follow-up evaluation.

Population pharmacokinetic analyses will be performed using plasma SEP-363856 concentrations; the results of which will be reported separately. The relationship between dopamine synthesis capacity and plasma SEP-363856 exposure using population

PK/pharmacodynamics (PD) methods will be explored. The plasma concentrations of the background antipsychotic medication will be examined based on bioanalytical determination, when available.

Exploratory evaluation of the effects of SEP-363856 on psychiatric symptoms will be based on change from baseline to Week 2 on the PANSS, CGI-S, and BNSS rating scales.

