## **8.2. Subject Exclusion Criteria**

To qualify for participation, subjects must not meet any of the following exclusion criteria at Screening and Day 1 (including all available predose assessments):

1. Subject answers “yes” to “Suicidal Ideation” Items 4 (active suicidal ideation with some intent to act, without specific plan) or Item 5 (active suicidal ideation with specific plan and intent) on the C-SSRS at or during the Screening period (ie, in the past one month) and/or Day 1 (ie, since last visit).
2. Subject does not tolerate venipuncture or has poor venous access that would cause difficulty for administration of the radioisotope and for collecting blood samples.
3. Subject is currently participating in, or has participated in, a study with an investigational or marketed compound or device within 3 months prior to signing the informed consent, or has participated in more than 2 studies of investigational compounds within 24 months prior to signing the informed consent.
4. Subject has participated in a research and/or PET or radiological investigations with radiation exposure that, when combined with the dose from the present study, would exceed 10 mSv in addition to natural background radiation, in the previous 12 months.
5. Subject has previously received SEP-363856.

6. Subject has any clinically significant unstable medical condition or any clinically significant chronic disease that in the opinion of the Investigator, would limit the subject's ability to complete and/or participate in the study:
  - a. Clinically significant hematological (including deep vein thrombosis) or bleeding disorder, renal, metabolic, endocrine, pulmonary, gastrointestinal, urological, cardiovascular, hepatic, neurologic, or allergic disease (except for untreated, asymptomatic, seasonal allergies at time of dosing).
  - b. Subject has a history of malignancy within 5 years prior to the Screening visit, except for adequately treated basal cell or squamous cell skin cancer or in situ cervical cancer. Subject has a pituitary tumor of any duration.
  - c. Disorder or history of a condition, or previous gastrointestinal surgery (eg, cholecystectomy, vagotomy, bowel resection) that may interfere with drug absorption, distribution, metabolism, excretion, gastrointestinal motility, or pH, or a history of clinically significant abnormality of the hepatic or renal system, or a history of malabsorption.

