### **11.9.2.2. Day -1**

The following procedures will be conducted for this Visit Day:

- Review Inclusion/exclusion criteria.
- Concomitant medications
- Vital sign measurements

- Perform psychiatric assessments in the following order: PANSS, BNSS, MADRS, CGI-S. (May be collected on Day -2)
- Perform C-SSRS. (May be collected on Day -2)
- Collect adverse events.

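### The C-SSRS schedule does not match the two rules that depend on it: no Day 1 rating for Exclusion 1, and none on Days 1 to 13 for the Type 4/5 discontinuation rule

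*Protocol*

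**What the plan says.** Two rules turn on the C-SSRS.

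- **Discontinuation.** Protocol 11.6.7.4 states: "Subjects with Type 4 or Type 5 suicidal ideation during the study will be discontinued from the study and referred to a mental health professional". The same section describes the scale as a means of tracking suicidal ideation and behaviour over the whole trial. SAP 16.6 repeats the rule and spells out Types 4 and 5.
- **Eligibility.** Exclusion 1 in Protocol 8.2 removes a subject who answers yes to ideation item 4 or 5 "on the C-SSRS at or during the Screening period (ie, in the past one month) and/or Day 1 (ie, since last visit").

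The schedule is set in three places.

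- **Protocol Table 2.** Footnote s reads "PANSS, BNSS, MADRS, CGI-S, and C-SSRS to be completed on Day -2 or Day -1". Footnote p adds that "C-SSRS should be performed prior to PET scan on Day 14".
- **Protocol visit lists.** The C-SSRS appears at Screening (11.9.1), Day -1 with Day -2 allowed (11.9.2.2), Day 14 (11.9.2.6), Follow-up (11.9.3) and early termination (11.9.4). The lists for Day 1 (11.9.2.3), Day 2 and on to Day 6 (11.9.2.4), and Day 7 and on to Day 13 (11.9.2.5) do not contain it.
- **SAP 16.6.** The scheduled C-SSRS visits are Screening, Day -1, Week 2 and Week 3.

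Footnote q to Table 2 calls for unscheduled BARS, AIMS and SAS ratings when extrapyramidal symptoms need treatment. No footnote or section does the same for the C-SSRS.

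**The concern.** Both rules are stated in terms of C-SSRS item levels, so each needs a C-SSRS at the time it is meant to apply. Exclusion 1 names Day 1, and no rating is planned on that day. The discontinuation rule covers the study as a whole, yet no rating is planned between first dose and Day 14, the planned day of the last dose.

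This matters for participants first. They enter with a PANSS total score of at least 70 and add a CNS-active compound to their antipsychotic. It also matters for reporting. The safety endpoint on frequency and severity of suicidal ideation rests, for the treatment period, on one retrospective interview per subject, apart from any early-termination rating or a repeat after a failed scan.

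**Working it through.** The documents give no figure to reproduce. The check is a comparison of texts and a count of study days. It rests on the visit lists, footnote s and SAP 16.6, which agree with each other, and not on column positions in Table 2.

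**Inputs**
- There is no Day 0: first dose is Day 1 and the day before it is Day -1 (SAP 7.1).
- Last predose C-SSRS: Day -2 or Day -1 (footnote s; 11.9.2.2).
- First scheduled C-SSRS after first dose: Day 14, before the PET scan (footnote p; 11.9.2.6).
- Dosing: once daily, Day 1 to Day 14. After an unsuccessful Day 14 scan it may continue, but not beyond Day 19 (7.1; 11.9.2.6).

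**Rule against schedule**

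| Rule | When it is meant to apply | Scheduled C-SSRS |
|---|---|---|
| Exclusion 1 | Screening and/or Day 1 | Screening; Day -2 or Day -1; none on Day 1 |
| Type 4/5 discontinuation | During the study | After first dose: Day 14 and Follow-up; early termination follows a decision to stop |

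**Intervals** (days from a to b = b − a, less 1 when the span crosses from negative to positive days)
- Last predose C-SSRS to first dose: 1 − (−1) − 1 = 1 day, or 1 − (−2) − 1 = 2 days.
- Last predose C-SSRS to the next scheduled one: 14 − (−1) − 1 = 14 days, or 14 − (−2) − 1 = 15 days.
- First dose to first scheduled on-treatment C-SSRS: 14 − 1 = 13 days.

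**Doses before the first scheduled on-treatment C-SSRS**
- Days 1 to 13 give 13 of 14 planned doses: 13/14 = 93%.
- Footnote p fixes the order against the scan but not against the dose, which is due about 2 to 4 hours before the scan. If the rating comes first, the Day 14 dose could be withheld. If it follows the dose, all 14 have been taken.
- If dosing runs to Day 19: 13/19 = 68% of doses come before the Day 14 rating. At most the Day 14 dose and the five doses on Days 15 to 19 could be spared.

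**Other routes to detection**
- Adverse events are collected on every dosing day (11.9.2.4, 11.9.2.5). Section 11.6.1 requires non-leading questions without specific prompting, so they do not ask the C-SSRS items or grade ideation as Type 4 or 5.
- Section 13.1 requires study treatment to stop when the Investigator judges that a subject can no longer take part safely. That is a judgement, not a structured assessment.
- SAP 16.6 would include an unscheduled C-SSRS in the post-baseline summary, but no text says when one should be done.

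**The case against.** The strongest reply is that the plan is safer than the rating schedule alone suggests, and much of that stands. Subjects are in clinic from Day -2, adverse events are collected daily, and the Investigator can stop treatment under Section 13.1. Exclusion 10, on risk of self-harm, applies on Day 1 without any C-SSRS. The Day 14 version asks about the whole interval since the last visit, the SAP takes the most severe post-baseline outcome, and protocol and SAP agree on the visits. No planned analysis fails.

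Three stronger readings are tempting, and the documents do not support them.

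1. *The Day 1 eligibility check is impossible.* The stem of 8.2 applies the "exclusion criteria at Screening and Day 1 (including all available predose assessments"), and the Day -2 or Day -1 rating is such an assessment. Exclusion 1 also says and/or, and Day 1 can be read as a label for Visit 2, which begins on Day -2. What remains is a mismatch with the Day 1 wording and one to two in-clinic days that the rating does not cover.
2. *The discontinuation rule can spare no dose outside an extension.* A C-SSRS done before the Day 14 dose could spare that dose. The rule is also not limited to scheduled ratings, so an unscheduled rating could act sooner, as could the Investigator's judgement under 13.1.
3. *The action texts conflict.* The synopsis and Section 7.1 say that subjects with significant findings "must be referred to the Investigator for follow-up evaluation". Section 11.6.7.4 adds a stricter consequence for Types 4 and 5. One is a general rule and the other a specific one, and both can be followed for the same subject.

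The reply does not supply the missing link. Unprompted reporting and judgement can raise suspicion, but neither produces the C-SSRS answer on which both rules are written. The plan sets a trigger for unscheduled movement scales and none for this one.

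**Conclusion.** The concern holds as a mismatch between two safety rules and the schedule meant to serve them. Exclusion 1 cites a Day 1 rating that is not scheduled. The rating that can stand in for it is one to two days old at first dose. The mandatory Type 4/5 discontinuation rule has no scheduled C-SSRS on Days 1 to 13 and no defined trigger for an unscheduled one. Thirteen of 14 planned doses come before the first scheduled on-treatment rating, 14 to 15 days after the previous one.

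These counts assume a subject who is dosed daily, has the Week 2 visit on Day 14 and does not terminate early. They describe scheduled ratings only. The finding does not show that ideation would go undetected, and it does not touch the primary PET endpoint. It is worth correcting because it bears on participant safety and is cheap to resolve.

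**What to change.** The sponsor and investigator should reconcile three sets of text:

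- Exclusion 1 in Protocol 8.2;
- the discontinuation rule in Protocol 11.6.7.4 and SAP 16.6;
- the C-SSRS schedule in Table 2 (with footnotes p and s), Protocol 11.9.2.2 to 11.9.2.6, and the visit and baseline definitions in SAP 16.6.

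After reconciliation, the assessments on which the rules depend should be scheduled, or have a stated trigger, whenever the rules are meant to apply. If the present schedule is intended, the rules should say which rating they rely on. The timing of assessments and the content of the clinical rule are for the sponsor and investigator to decide.

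The cost is wording changes in both documents and possibly an extra rating on an existing in-clinic day. Section 11.6.7.4 puts the scale at about five minutes.
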